GIRLS INVEST

Methods Protocol

CLINICAL TRIALS UNIQUE ID: NCT06942481

April 23, 2025

METHODS

This study involved a two-arm cluster randomized controlled trial among 258 adolescent females ages 15-19 years in 16 secondary schools within low-income communities from two Local Government Areas (LGAs) with the highest concentration of low-income communities within Ibadan, Nigeria. Low-income communities were of particular focus considering the intersection of economic vulnerability and IPV risk^{1,2}. Sixteen schools within low-income communities were selected from the 28 schools approved by the Ministry of Education; schools were randomized to treatment assignment (Girls Invest intervention or wait-list control group) using a randomizer software package after baseline data collection. The wait-list control groups were provided with referrals to local support organizations, as the standard of care, and received Girls Invest subsequent to the six-month follow-up data collection. The study protocol was approved by the Human Research Protection Program at San Diego State University (HS-2021-0031) in the US and the University of Ibadan / University College Hospital Joint Institutional Review Board, in Nigeria (UI/EC/21/0183). Letter of approval was obtained from the Oyo state Ministry of Education, Nigeria and permission obtained from the Principals of each school.

Intervention Description

The Girls Invest intervention involved: 1) app-based trainings on topics related to financial literacy, gender equity, and health and 2) financial resources/incentives supporting girls' education/career.

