Surveys were conducted with all participants at baseline and at a six-month follow-up timepoint. The survey collected data on girls' experiences of IPV, gender-based attitudes, and perceptions of economic vulnerability as well as demographic characteristics. Research staff administered the survey in a one-on-one private setting. The survey took about 45 minutes to complete; participants received N4,000 for the baseline survey and N6,000 for the follow-up survey as compensation for their time. The follow up rate was 69% among intervention and control groups, with no significant difference in follow-up by treatment group ($p=0.72$).

Focus group participants ($n=62$; approximately 12-13 participants in each of 5 focus groups) were drawn from study participants who had completed the Girls Invest intervention. Participation was voluntary and demographics matched those of the larger sample. After completing the six-month follow-up survey, participants who voiced interest in participating in the focus groups were contacted to schedule the focus group. Trained and experienced facilitators conducted informed consent among all focus group

participants and subsequently conducted the focus group, which lasted about 60-90 minutes and took place in a private room. Participant satisfaction and acceptance of the intervention were assessed, as well as how app-based trainings impacted participants' knowledge, attitudes, and beliefs regarding Girls Invest topics. Participants were reimbursed N6,000 upon completion of the focus group discussions. Focus group discussions were digitally recorded, transcribed, and de-identified.

Measures

Program monitoring data were automatically downloaded from the app, generating a spreadsheet providing information on module completion, including the time spent on each module. Additional process data were recorded by research staff regarding the provision of the financial incentives upon app-based training completion, including the type of financial incentive received.

Survey measures included sample characteristics as well as gender attitudes and economic factors associated with IPV.

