A difference-in-differences approach was used to assess changes between baseline and follow-up in: 1) attitudes supportive of traditional gender roles, 2) attitudes supportive of IPV, 3) coping with experiences of gender-based discrimination, and 4) perceptions of economic vulnerability. The primary analysis was conducted using a linear regression model with cluster-adjusted standard errors to account for intra-cluster correlation. The model included an interaction term between time (pre/post) and study arm (intervention/control) to estimate changes over time associated with the intervention. Given that there were no statistically significant differences in demographic factors at baseline between the intervention and control groups (indicating effective randomization of treatment group assignment), we did not include covariates in the models. Analyses used an intention-to-treat (ITT) approach, with sensitivity analyses conducted to assess robustness to missing data and alternative model specifications. All analyses were performed using SAS v9.4.

For analyzing the focus group data, an inductive, content analysis approach was used. Content analysis involves generating and applying codes to sections of text, then reviewing the text by various codes and 'code families' to identify recurring themes. The coding team created an initial list of codes based on key domains and used these to code discussions. To enhance coding agreement, data were individually coded by two researchers, and coding procedures and definitions were discussed and compared for agreement. Additions of new codes or changes in code definitions were determined via consensus among the research team. Additional codes related to participants sharing information they learned in the app trainings were created to reflect these emerging themes. No new codes emerged after two-thirds of the focus groups were coded, suggesting that content saturation was achieved. For this particular analysis, we retrieved coded text on themes related to acceptability with the program as well as economic and social impacts. Inter-coder reliability was assessed, with 80% coder consistency or higher between coders deemed sufficient for inter-coder reliability.

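### The time-by-arm regression subtracts each outcome's baseline arm difference at a fixed weight of 1; adjusting for the baseline score already collected would usually be more precise

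*Combined protocol and SAP*

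**What the plan says.** The design is described at the start of the Methods as a "two-arm cluster randomized controlled trial among 258 adolescent females ages 15-19 years in 16 secondary schools". On timing, "schools were randomized to treatment assignment (Girls Invest intervention or wait-list control group) using a randomizer software package after baseline data collection".

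Under Data Collection Procedures, "Surveys were conducted with all participants at baseline and at a six-month follow-up timepoint", and "The follow up rate was 69% among intervention and control groups".

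Under Data Analysis, "The primary analysis was conducted using a linear regression model with cluster-adjusted standard errors to account for intra-cluster correlation". The effect comes from the interaction: "The model included an interaction term between time (pre/post) and study arm (intervention/control) to estimate changes over time associated with the intervention". Non-significant demographic differences at baseline are given as the reason for leaving covariates out: "indicating effective randomization of treatment group assignment), we did not include covariates in the models". Further analyses are mentioned only in general terms, "with sensitivity analyses conducted to assess robustness to missing data and alternative model specifications"; none is named. No random effects or working correlation are stated, so ordinary least squares on person-time rows is the natural reading, though it is an inference.

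**The concern.** With two arms, two time points and no covariates, the interaction coefficient is the follow-up arm difference minus the whole of the baseline arm difference. Randomisation after baseline makes that baseline difference pure chance, so its expected value is zero. Subtracting some of it removes noise to the extent that baseline predicts follow-up. Subtracting all of it overcorrects unless baseline and follow-up are almost perfectly correlated at the level that drives the variance.

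The stated reason for omitting covariates does not address this. It concerns demographic factors, not the baseline value of each outcome. The case for adjustment also rests on how well a variable predicts the outcome, not on whether the arms differ significantly at baseline. That is a point of wording and changes no result by itself.

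What is at stake is precision in a small trial, using data already in hand. The documents state no power target, so none is shown to be missed.

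**Working it through.** **Inputs from the documents.** 258 girls, 16 schools, 69% followed up: 0.69 × 258 ≈ 178 girls, about 11 per school. The baseline survey covered all participants. There is no stated power, SD, ICC or correlation to reproduce.

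**Assumed.** Eight schools per arm, loss at random, girl-level correlation 0.3–0.75, ICC 0–0.10, school-effect correlation over time 0.5–1.0.

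**Step 1: the weight.** In simulated data with 31% of follow-up missing, the interaction coefficient equalled (follow-up difference) − 1 × (baseline difference) to 1e-9.

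**Step 2: closed form, ignoring clustering.** With equal variances, correlation ρ and weight w on the baseline difference, the variance is proportional to 1 + w² − 2wρ.
- At w = 1 it is 2(1 − ρ).
- At the best weight, w = ρ, it is 1 − ρ².
- The ratio is (1 + ρ)/2.

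If the planned model keeps all baseline rows with 69% followed up, its factor becomes 1 + 0.69(1 − 2ρ):

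| ρ | Planned | Adjusted | Ratio |
|---|---|---|---|
| 0.3 | 1.276 | 0.910 | 0.71 |
| 0.5 | 1.000 | 0.750 | 0.75 |
| 0.7 | 0.724 | 0.510 | 0.70 |

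**Step 3: clustering shrinks the gain.** With m = 11.13 girls per school, the correlation of school means is r = [m·ICC·(school correlation) + (1 − ICC)·(girl correlation)] / [1 + (m − 1)·ICC]. At ICC 0.05, school correlation 0.8 and girl correlation 0.5:
- r = (0.445 + 0.475)/1.506 = 0.611.
- (1 + r)/2 = 0.805.
- Multiplying by 13/12, for a slope estimated from 16 schools, gives 0.87.

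**Step 4: simulation.** 80 settings, 6,000 runs each. Schools were equal (16–17 girls) or unequal (minimum 5). Entries are the variance of the model with girl baseline and school-mean baseline, divided by that of the planned model:

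| Planned model uses | Girl correlation | Equal schools | Unequal schools |
|---|---|---|---|
| All baseline rows | ≤ 0.6 | 0.770–0.941 | 0.772–0.977 |
| All baseline rows | 0.75 | 0.726–0.822 | 0.737–0.827 |
| Completers only | ≤ 0.6 | 0.725–0.946 | 0.713–0.991 |
| Completers only | 0.75 | 0.879–1.016 | 0.876–1.031 |

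- Against all rows the variance cut is 2–27%, or 1–15% in the SE.
- Against completers only, a loss occurs in 3 of 80 settings, all at correlation 0.75 with perfectly stable schools.
- At ICC 0.20 the completers-only ratio reaches 1.06, and 1.08 in separate runs; it is already 1.03 at correlation 0.6.
- The planned estimate showed no bias (largest absolute mean 0.006).

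**Step 5: detectable difference.** At girl correlation 0.45, ICC 0.05, school correlation 0.8 and equal schools, the ratio is 0.88. Then 0.51 × √0.88 ≈ 0.48 SD at 80% power. The lost degree of freedom (14 to 13; t 2.145 to 2.160) costs about 1.5% on the variance scale and leaves the result at about 0.48.

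**Step 6: why the school mean is needed.** Adjusting for girl baseline alone gives 0.68–1.18 against all rows, and up to 1.55 at ICC 0.20. Taking the school mean from followed-up girls only worsens the worst case from 0.977 to 1.025.

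**Step 7: inference.** Type I error at nominal 5%, in three settings:
- Adjusted model, ordinary cluster-robust SE: 9.8–10.6% with z, 7.3–8.0% with t on 13 df.
- Planned model, same SE, t on 14 df: 5.8–7.0%.
- Adjusted model, permutation of school assignments: 4.8–5.5%.

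**The case against.** Difference-in-differences is a valid, standard estimator here, and no error is shown. The benefit of the alternative depends wholly on parameters the documents do not give. Data collection ended in July 2024 and the analyses are described as performed, so a second, more sensitive test on four outcomes comes late. The unnamed sensitivity analyses may already include it.

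The usable gain can also be smaller than the variance ratios suggest. With the plan's own kind of SE, the adjusted model's type I error is worse, so the change requires better inference as well. In simulated power at 0.5 SD (girl correlation 0.45, ICC 0.05, school correlation 0.8), the planned test on 14 df gave 78.8% with equal and 78.4% with unequal schools. The adjusted permutation test gave 82.9% and 79.5%. With permutation for both, the gain was about 5–7 points. With unequal, perfectly stable schools (girl correlation 0.3, ICC 0.10), permutation gave 80.7% planned and 80.1% adjusted: no gain.

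Most of this stands as a limit on size and timing. It does not remove the point: the primary model is the less efficient one in most plausible settings, and no baseline-adjusted analysis is named. The documents also make the loss region less likely. The Measures section gives Cronbach alphas of 0.60, 0.65 and 0.60 for three of the four scores. If alpha approximates reliability, a six-month correlation of 0.75 is implausible for those three. The same reasoning lowers the largest plausible cut against all rows for those scores from 27% to about 23%.

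**Conclusion.** The concern holds. The planned coefficient uses a fixed weight of 1 on a chance baseline difference, and adjusting for girl and school-mean baseline would usually be more precise. The size is modest and cannot be fixed from the documents; 72 of the 80 settings show a cut of 5–25% against the all-rows model, but that counts a chosen grid and is not a probability. Once the lost degree of freedom is counted, 5 of 80 settings show no gain over a completers-only model and none fails to gain over an all-rows model.

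This rests on an ordinary least squares reading, 8:8 allocation and loss at random. If loss depends on baseline score differently by arm, the two methods could also differ in bias, which is a separate question. The planned result is not invalidated.

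**What to change.** For each of the four outcomes, regress the six-month score on arm, the girl's own baseline score and the school-mean baseline score. Compute that mean from all girls surveyed at baseline. Report the result beside the difference-in-differences estimate, and label it post hoc if results had already been seen.

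Base inference on permutation of school assignments applied to this girl-level regression, following the allocation scheme actually used. The documents name only a randomiser package, so the scheme has to be stated. If t on 13 df is used instead, pair it with a small-sample-corrected SE. An unweighted regression of 16 adjusted school means held type I error at 4.0–5.6%, but with unequal schools its variance ratio to the all-rows model ran from 0.77 to 1.24, so it can lose the gain.

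State whether the planned model uses all baseline rows or completers only. Name the alternative specifications that were run. Reword the covariate sentence so that the choice does not rest on baseline significance tests.

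The cost is SAP wording and a re-run on existing data, plus one school-level degree of freedom. The roughly 80 girls without follow-up enter only through the school mean, though their outcome is missing under either model.
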